### 6.3.2.3. Humphrey Visual Field

The visual field will be measured by Humphrey Visual Field analysis (24-2 SITA-Standard) including standardised refraction as indicated, according to the Visual Field Centre SOP (Manual of Procedures).

- At screening HVF will be reviewed by the Visual Field Reading Centre to confirm eligibility.
- Inability to perform a reliable visual field examination as deemed by the Visual Field Reading Centre in study eyes (including >15% false positives), is an exclusion criterion. HVF can be repeated to obtain an assessment with reliable performance.
- If the site is concerned with the HVF findings, suggesting that the patient is a treatment failure and may require rescue therapy, the Visual Field Reading Centre review will be prioritised and when indicated expedited to the IAC.

### 6.3.2.4. Visual Acuity

Assessment of visual acuity will be recorded using a LogMAR chart (unaided, best corrected, and with pin hole).

### 6.3.3. Headache Assessments

Patients will be provided with an electronic/paper diary at screening to complete during the trial. Information collected will be used to assess the following headache parameters:

- Monthly headache days
- Monthly moderate to severe headache days
- Responder rate
- Monthly acute analgesic use
- Headache severity (11-point NRS)

#### 6.3.3.1. Headache Preventative Medication Review

A review of any headache preventative medications taken by the patient will be undertaken at each clinic visit. If the Investigator alters the headache preventative medication, this will be considered rescue medication (Section 10.1.1) and the IAC consulted. Use of headache preventative medication will be recorded at trial visits as outlined in the Time and Events table (Table 1).

Study Number: INVEX-CLIN-IIH-301 Protocol	Compound No.: Presendin
	Version: 5.0 for EU countries dated 08Dec2022

Patients will record their acute headache analgesic use in their trial diary.

### **6.3.4. Patient Reported Outcomes**

#### **6.3.4.1. Visual related**

Assessment of visual related quality of life will be derived from self-reported responses to the VFQ-25-10 item supp (see Section 16.6 Appendix 6).

#### **6.3.4.2. Health-related**

Assessment of health-related quality of life will be derived from self-reported responses using the following questionnaires:

- 36-item short form survey
- EuroQol -5 dimension -5 level survey

A Healthcare Utilisation Form will be completed by the trial site staff at clinic visits.

All questionnaires can be found in Section 16, Appendix 3 for SF-36 and Appendix 4 for the EuroQoL- 5D-5L survey.

#### **6.3.4.3. Headache related Quality of Life**

Assessment of headache-related quality of life will be derived from self-reported responses to the Headache Impact Test-6 questionnaire and performed at time points as outlined in the Time and Events table (Table 1). A copy of this questionnaire can be found in Section 16.5, Appendix 5.

#### **6.3.4.4. Patient Global Impression of Change**

The Patient Global Impression of Change will be conducted at visit 10, as outlined in the Time and Events table (Table 1).

It is a single item questionnaire using a seven-point verbal response scale to assess overall change in the patient's status since taking trial medication. A copy of this questionnaire can be found in Section 16.7, Appendix 7

### **6.3.5. Body Weight and Body Mass Index**

The patient's body weight and BMI will be measured at the time points as outlined in the Time and Events table (Table 1).

The patient's height will be measured at Screening (shoes off).

Study Number: INVEX-CLIN-IIH-301 Protocol	Compound No.: Presendin
	Version: 5.0 for EU countries dated 08Dec2022

## 7. SAFETY MEASURES DUE TO A GLOBAL CRISIS

The COVID-19 global pandemic presents numerous challenges to the conduct of ongoing clinical trials. In line with the FDA and European Medicines Agency's Guidance on the Management of Clinical Trials During the COVID-19 (Coronavirus) Pandemic (EMA, 2021), the following protocol considerations are provided to ensure patients safety is maintained and adequate benefit/risk analyses are applied relative to the completion of study procedures and maintaining the investigational product supply chain.

Recognizing the flexibility required to manage the impact of the pandemic (or other global crisis) on this clinical study, additional details will be added to respective study manuals, project plan documents, and communicated to the investigative sites as needed. For any additional questions, the investigator should confer with the sponsor.

### Number of Trial Patients

The evolving situation of the pandemic (or other global crisis) may result in a substantial number of patients' early withdrawal from the study, which could affect the data integrity of the study. Because of this risk, the sponsor may decide to recruit additional patients in the study, beyond the expected number, to mitigate such risk.

### Study Visits

There are a number of on-site visits that would be required to ensure study validity. If there are local travel restrictions, isolation requirements, or the investigator determines it to be unsafe for patients to attend their scheduled study visits, the site staff may conduct certain visits via telemedicine (phone or video calls) to minimize patient risk as follows.

### *Screening Period*

The following visit must be performed in person:

- Screening/Visit 1

Note: To minimize direct, in-person contact between site personnel and patients, certain screening procedures may be performed remotely via telemedicine. All other procedures should be done in-person while the subject is on-site.

Specifically, the following procedures may be done remotely:

- Informed consent (where applicable, per approved IRB/IEC process)
- Demography
- Medical and ophthalmic history
- Concomitant medication history

Study Number: INVEX-CLIN-IIH-301 Protocol	Compound No.: Presendin
	Version: 5.0 for EU countries dated 08Dec2022

- Headache history
- Headache preventative medication review
- Train and dispense headache diary
- Trial medication training

*Randomised period*

- Baseline (Visit 2)

There are essential aspects to the baseline visit which must be performed in person.

If the baseline visit is delayed the headache diary should utilise the preceding 7 days data. Where the visit is delayed by more than 10 days due to a global crisis the patient will be considered to have failed screening. Patients who screen failed due to the pandemic (or other global crisis) may be rescreened at a later time, if feasible.

To minimize direct, in-person contact between site personnel and patients, certain procedures may be performed remotely via telemedicine. All other procedures should be done in-person while the subject is on-site. Specifically, the following procedures may be done remotely:

- Concomitant medication review
- Headache preventative medication review
- Headache diary review
- Adverse events
- Patient reported outcomes
- Health utilisation form

- Visit 4, 5, 6, 7, and 8

There are essential aspects to these visits which must be performed in person.

Where this is not possible due to the pandemic or other global crisis the following components of the visit should be performed at the next available opportunity in line with the schedule of assessments table:

- Vital signs
- Body weight and BMI
- Physical examination
- Urine pregnancy test

Study Number: INVEX-CLIN-IIH-301 Protocol	Compound No.: Presendin
	Version: 5.0 for EU countries dated 08Dec2022

- Electrocardiogram
- Optical coherence tomography imaging
- Humphrey Visual Field
- Visual acuity testing
- Laboratory assessments
- Pharmacokinetic sampling
- Anti-drug antibodies sampling

To minimize direct, in-person contact between site personnel and patients, certain procedures may be performed remotely via telemedicine. All other procedures should be done in-person while the subject is on-site. Specifically, the following procedures may be done remotely:

- Concomitant medication review
- Headache preventative medication review
- Headache diary review
- Adverse events
- Patient reported outcomes
- Health utilisation form

- Visit 10

There are essential aspects to these visits which must be performed in person. Where this is not possible due to the pandemic or other global crisis the following components of the visit should be performed at the next available opportunity in line with the schedule of assessments table:

- Vital signs
- Body weight and BMI
- Physical examination
- Urine pregnancy test
- Electrocardiogram
- Optical coherence tomography imaging
- Humphrey Visual Field
- Visual acuity testing
- Laboratory assessments
- Pharmacokinetic sampling
- Anti-drug antibodies sampling
- Lumbar puncture\*

Study Number: INVEX-CLIN-IIH-301 Protocol	Compound No.: Presendin
	Version: 5.0 for EU countries dated 08Dec2022

\* Lumbar puncture to be ideally performed after visual assessments. In the 4 weeks prior to visit 10, patients must not have missed more than one dose of trial medication and must have self-administered their final dose within 7 days of visit 10. Patients will be reminded by the trial site to self-administer trial medication weekly, to continue this until the completion of visit 10 and to bring their trial medication with them at visit 10 for return.

Where more than one dose has been missed during the preceding 4 weeks, visit 10 should be delayed. Self-administration of trial medication should continue at 7-day intervals and then visit 10 rescheduled to ensure no more than one dose of the trial medication has been missed in the previous 4 weeks. Visit 10 should be delayed no more than 14 days, if possible, but this can be extended according to local government policy if a patient is unable to attend (for example if a patient is self-isolating) as long as medication use is maintained as above.

- Follow up/ Visit 11

This should be performed as a telephone visit unless clinical contact is necessary, as per protocol. Where face to face contact is required, this should be conducted at the earliest available opportunity.

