Visit	SCREENING PERIOD 	RANDOMISED PERIOD 									FOLLOW UP	
	V1 Clinic	V2 Clinic Baseline	V3 TC	V4 Clinic	V5 Clinic	V6 Clinic	V7 Clinic	V8 Clinic	V9 Clinic	V10  Clinic		Unscheduled repeat visual assessments 
Visit Window (days)		+3	± 1	± 3	± 3	± 5	± 5	± 5	± 5	± 14		± 5
Month	0	0			1	2	3	4	5	6		
Week	-1	0		2	4	8	12	16	20	24		29
Day	-7	1	3	15	29	57	85	113	141	169		204
Pharmacokinetic (PK) sampling 		X 		X	X	X	X	X	X	X		
Anti-Drug Antibodies (ADA) sampling		X		X	X	X	X	X	X	X		
Lumbar Puncture 										X 		
Trial medication training 	X	X										
Randomisation		X										
Trial medication Dispensing	X	X			X	X	X	X	X			
Trial medication Accountability				X	X	X	X	X	X	X		

 The screening period must be a minimum of 7 days, up to a maximum of 10 days. Patients who do not meet the eligibility criteria based on diary review at randomisation/baseline (e.g., too few headache days or unacceptable concomitant medication use) will be considered screen failures; however, if the patient wishes and the Investigator is in agreement, he/she can be re-screened as a new patient. If the screening period exceeds 7 days, then eligibility will be based on the last 7 days of the screening period, i.e., the 7 days prior to randomisation visit. Trial site research team should review diaries remotely on a weekly basis to ensure compliance and follow up any patients with missing data

 Vital signs to include: blood pressure and heart rate

 Women of child-bearing potential. Serum pregnancy test to be conducted at screening, thereafter, highly sensitive urine pregnancy tests will be conducted. Visit 11 urine pregnancy test may be conducted at home

 Frisén grade will be evaluated locally and the presence of papilloedema verified by the OCT Reading Centre at screening to confirm eligibility. Indeterminate cases should be referred to the IAC (and supplemented with fundus photography and ultrasound scan of the optic nerve) to confirm papilloedema prior to randomisation visit

 Haematology, coagulation, biochemistry and urinalysis

 All actual sampling times and dosing times will be recorded

 Baseline Post-dose PK blood sample

Study Number: INVEX-CLIN-IIH-301 Protocol	Compound No.: Presendin
	Version: 5.0 for EU countries dated 08Dec2022

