## 6. TRIAL ASSESSMENTS AND PROCEDURES

### 6.1. Procedures at Each Visit

Trial procedures and timings are presented in the Time and Events Table, [Table 1](#).

No procedures should be performed prior to obtaining informed consent. All visits (except telephone call visits) should be performed at the clinic. Should a clinic visit not be possible, due to a patient self-isolating, the visit will be conducted at the earliest opportunity and will not constitute a protocol deviation.

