### **Study Drug Dispensation and Distribution**

If a patient is not able to attend a clinic visit, to ensure the continuity of providing patients' study drug within the constraints imposed by the pandemic (or other global crisis), the site staff may decide to supply study drug to patient as follows:

- Adequate supplies of study drug can be shipped to the patient by the study staff using a third-party service with approval from the patient. The third-party vendor will be agreed upon with the sponsor.
- The patient may request, with prior arrangement/agreement with the site, an authorized individual (a relative or delegate) to retrieve the study drug from the study site if the patient is unable to personally to do so.

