### **Direct Contracts with Third Parties/Specialized Service Companies**

If necessary, direct contracts can be established with third-party local physicians to conduct activities related to the clinical management of patient for whom the investigator is responsible and maintains oversight. In such situations, the investigator is required to provide the local physician with a delegation letter listing all delegated activities. The sponsor, through the study investigator or institution, will reimburse the local physician for the test/procedures conducted outside of the standard of care.

Clinic visits should take place to the extent possible and usual protocol requirements adopted for all subjects as soon as the crisis-related limitations permit.

All safety data that are possible to obtain locally should be collected at a remote visit. These measurements may include the use of local practitioners and resources.

Exceptional measures taken in response to a crisis (e.g., COVID-19) and their impact on study results, such as tests done in a local laboratory, will be explained, assessed and reported in the clinical study report following ICH E3 guidance.

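### Section 7 defers the urine pregnancy test at crisis-affected Visits 4–8 and 10 while dosing may continue, and its own general clause on local safety data points the other way

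*Protocol*

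**What the plan says.** Table 1 and Section 6.1.4 schedule a urine pregnancy test for women of childbearing potential at every clinic visit during treatment. Section 7 changes this when a crisis stops a patient attending.

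- **Visits 4–8.** Where attendance is not possible, "the following components of the visit should be performed at the next available opportunity in line with the schedule of assessments table". The urine pregnancy test is on the list that follows, and no maximum delay is given. A separate list names six procedures that may be done remotely, and the pregnancy test is not one of them. For the rest the block says "All other procedures should be done in-person while the subject is on-site".
- **Visit 10.** The test is again on the deferred list. The delay is limited to 14 days where possible, but "this can be extended according to local government policy if a patient is unable to attend", provided dosing is kept up. This block has no remote list.
- **Drug supply.** When a clinic visit is missed, "Adequate supplies of study drug can be shipped to the patient by the study staff using a third-party service with approval from the patient", or a delegate may collect the drug.
- **General clause.** Under the heading on third-party contracts: "All safety data that are possible to obtain locally should be collected at a remote visit". The next sentence allows local practitioners and resources to be used.
- **Manuals.** Section 7 opens by saying that "additional details will be added to respective study manuals, project plan documents, and communicated to the investigative sites as needed".
- **Home testing elsewhere.** Footnote 3 of Table 1 states "Visit 11 urine pregnancy test may be conducted at home", and Section 6.1.6 says the same for a telephone visit.

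**The concern.** IIH occurs mostly in women of childbearing age (Section 1.1). Section 1.1.2 reports an effect of Byetta on foetal development in animals at three times human exposure. Section 6.2.2.4.5 stops treatment once pregnancy is identified, so a test result directly changes dosing. The scheduled test does not prevent pregnancy. It shortens exposure in a woman who does not yet know that she is pregnant.

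The crisis rules protect drug supply but do not tie it to this test. A site that follows the visit-specific list can send drug home while the test waits. Unlike the ECG, perimetry, OCT and blood samples on the same list, a urine test can be done at home, as the protocol itself recognises for Visit 11.

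**Working it through.** The plan states no figure on this point. The check is a comparison of texts and then arithmetic on the visit schedule.

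**1. The two instructions for a patient who cannot attend Visits 4–8**

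| Source in Section 7 | What it implies for the urine pregnancy test |
|---|---|
| Deferred list, Visits 4–8 | Wait until it can next be done |
| Remote list, Visits 4–8 | Not included |
| In-person default, Visits 4–8 | Do it on-site |
| General clause on local safety data | Do it locally now, if obtainable |

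The first three are specific and point to deferral. The fourth is general, does not name the test, and points to a local test. At Visit 10 only the deferred list and the general clause apply.

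**2. Intervals between tests**

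Inputs are the nominal days in Table 1: Visit 2 Day 1, Visit 4 Day 15, Visit 5 Day 29, Visit 6 Day 57, Visit 7 Day 85, Visit 8 Day 113, Visit 9 Day 141, Visit 10 Day 169.

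Planned gaps: 15 − 1 = 14; 29 − 15 = 14; then 57 − 29 = 28, and 28 for each later gap.

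The interval if visits are missed and no local test is done is the day of the next test minus the day of the last test. The number of doses is that interval divided by 7, counting the dose taken on the day of the last test and assuming weekly dosing from Day 1.

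| Missed | Interval (days) | Weekly doses |
|---|---|---|
| None (monthly visits) | 57 − 29 = 28 | 4 |
| Visit 4 | 29 − 1 = 28 | 4 |
| Visit 5 | 57 − 15 = 42 | 6 |
| Visit 6 | 85 − 29 = 56 | 8 |
| Visit 7 | 113 − 57 = 56 | 8 |
| Visit 8 | 141 − 85 = 56 | 8 |
| All of Visits 4–8 | 141 − 1 = 140 | 20 |
| Visit 10 delayed 14 days | 183 − 141 = 42 | 6 |

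A longer extension of Visit 10 has no numerical limit. Visit 4 dispenses no drug (Table 1), so shipment matters from Visit 5 onward.

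**3. Added risk**

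Input: criterion 9 in Section 5.2.1 requires contraception with a failure rate below 1% per year when used consistently and correctly. The women affected by a missed test are those who would have tested positive at it.

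- One missed visit among Visits 6–8 adds 28 days: 1% × 28/365 = 0.08% per woman.
- All of Visits 4–8 missed: the last skipped test is Day 113, so the window is 113 − 1 = 112 days, and 1% × 112/365 = 0.31% per woman.

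Both are upper limits under correct use. They take no credit for a woman recognising the pregnancy herself.

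**4. After the fix**

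With a home or local test at each remote visit, the nominal intervals return to 14 and 28 days.

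**The case against.** The strongest reply is that Section 7 already provides for the test. A urine pregnancy test is plainly safety data that can be obtained locally, and the general clause covers all such data. The in-person sentence can be read as dividing up the work of an attended visit, and the deferred list does not say that the test must wait for the clinic. On that reading a manual could specify home kits without contradicting anything, and the manuals are not shown.

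This has force and lowers the stakes, but it does not remove the problem. The deferred list names the pregnancy test; the general clause does not. A site reading the block for its own visit would reasonably defer.

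Other points also stand. Shipping drug is at the site's discretion, so a site may test first. A pregnant woman must tell the investigator at once (Section 13.5), although this helps only when she knows. Remote adverse-event review is a weak substitute, because Section 13.5 does not generally treat pregnancy as an adverse event. Visit 11 falls after dosing, so preferring a clinic test during dosing is defensible where the clinic can be reached.

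**Conclusion.** The point holds as a minor safety and drafting matter. The protocol gives conflicting instructions on the urine pregnancy test at crisis-affected Visits 4–8 and 10, and the more specific instruction is to defer it while dosing may continue. The test interval becomes 56 days for one missed visit among Visits 6–8 and up to 140 days if all of Visits 4–8 are missed. These figures assume nominal visit days and no local testing. The added risk from 28 further days is at most about 0.08% per woman, assuming correct contraceptive use. Endpoints, estimands, error rate and power are untouched.

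A reader might infer more than the text supports:

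- **Gaps of 168 or 182 days.** These need Visit 9 to be missed too (169 − 1 and 183 − 1). Visit 9 is not on the deferred lists; for it, Section 6.1 says only that, for a self-isolating patient, "the visit will be conducted at the earliest opportunity and will not constitute a protocol deviation".
- **A remote list at Visit 10 that omits the test.** Visit 10 has no remote list; there the test is simply deferred.
- **No provision at all for a remote test.** The general clause supports one.
- **The chance of any pregnancy over a whole interval as the cost of deferral.** At the 1% ceiling this is 0.15% over 56 days (1% × 56/365), but a 28-day wait is already part of the normal schedule, so only the added days count.

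**What to change.** In Section 7, take the urine pregnancy test off the deferred lists for Visits 4–8 and Visit 10. Require it at home or through a local practitioner at each remote crisis visit while the patient is dosing. Send a kit with the shipped drug and have the site confirm the result by phone. This agrees with the general clause and with what is already accepted at Visit 11. Extend the Visits 4–8 block to Visit 9, which Section 6.1.4 groups with those visits but Section 7 leaves without a block of its own.

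The cost is a short amendment and the kits. A home test reported by phone is slightly less controlled than a clinic test, so the clinic test should remain the rule whenever the patient can attend.

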### **Study Drug Dispensation and Distribution**

If a patient is not able to attend a clinic visit, to ensure the continuity of providing patients' study drug within the constraints imposed by the pandemic (or other global crisis), the site staff may decide to supply study drug to patient as follows:

- Adequate supplies of study drug can be shipped to the patient by the study staff using a third-party service with approval from the patient. The third-party vendor will be agreed upon with the sponsor.
- The patient may request, with prior arrangement/agreement with the site, an authorized individual (a relative or delegate) to retrieve the study drug from the study site if the patient is unable to personally to do so.

